1. LIST OF ABBREVIATIONS

Abbreviation	Definition
13vPnC	13-valent pneumococcal conjugate vaccines
7vPnC	7-valent pneumococcal conjugate vaccine
AE	Adverse Event
AEFIS	Adverse event following immunization information system
AEM	Adverse event monitoring
CDC	Centers for disease control and prevention
EHR	Electronic health record
EMR	Electronic medical record
НСР	Healthcare Professional
HGRAC	Human Genetic Resources Administration of China
Hib	Haemophilus influenzae type b
ICD-10	International classification of diseases, tenth revision
IEC	Independent ethics committee
IPD	Invasive pneumococcal disease
IPV	Inactivated polio
IRB	Institutional review board
NID	National identification
NIS	Non-interventional study
NMPA	National Medical Products Administration
PAC	Post authorization commitment
PPV	Positive predictive value

[figure not shown]
Abbreviation	Definition
RV	Rotavirus
SAP	Statistical analysis plan
SOI	Safety outcome of interest
SOP	Standard operating procedure

3. AMENDMENTS AND UPDATES

Amendment number	Date	Substantial or administrative amendment		Protocol section(s) changed		Summary of amendment(s)		Reason
	12 December 2018	Substantial	•	Section 1, 5, 6, 8, and 9. Section 2. Section 7.	•	Editorial changes by abbreviating some terms such as safety outcomes of interest, changing CFDA to NMPA. Changed names of three investigators. Re-estimated the study size based on the new data.	•	To update the protocol and make it concise. To reflect on the change in study personnel. The original study size was estimated based on the annual birth rate and the coverage for Prevenar 7. The new exposure data showed the coverage for Prevenar 13 is much higher than Prevenar 7. In order to renew the HGRAC application, it is necessary to re-estimate the study size.
2	30 January 2019	Administrative	•	Section 7	•	Re-estimated the study size based on the more current data.	•	In order to renew the HGRAC application, it is necessary to re estimate the study size.

4. MILESTONES

Milestone	Planned date
Start of data collection (first data cut)*	15 December 2018
End of data collection (last data cut)*	30 September 2020
Study progress report 1	15 April 2018
Study progress report 2	15 April 2019
Study progress report 3	15 April 2020
Final study report	15 April 2021

^{*}For the main study.

5. RATIONALE AND BACKGROUND

Pneumococcal disease is a leading cause of serious illness throughout the world.¹ It is an infection caused by *Streptococcus pneumoniae* bacteria ("pneumococcus"). These bacteria can result in both invasive diseases such as bacteremic pneumonia, septicemia, and meningitis, and non-invasive diseases, such as pneumonia, otitis media, and sinus infections. One of the key risk factors of pneumococcal diseases is age, with children younger than 2 years of age and the elderly being at the highest risk of developing pneumococcal-related infection.¹ Pneumococcal disease is estimated to be the leading cause of vaccine-preventable morbidity and mortality among children younger than 5 years both globally and in China.¹ At least 1 million children die of pneumococcal disease every year, most of these being young children in developing countries.² In China alone, approximately 30 thousand children in this age group die due to pneumococcal disease every year.³

Currently, several approved vaccines to prevent *S. pneumoniae* infections are available on the market, including the 10-, and 13-valent pneumococcal conjugate vaccines (10vPnC; Synflorix, GlaxoSmithKline and 13vPnC; Prevnar 13, Pfizer, respectively), and the 23-valent pneumococcal polysaccharide vaccine (PPSV23; Pneumovax, SanofiPasteurMSD [in the US, Merck]). 13vPnC was approved in the European Union in December 2009 for the prevention of Invasive Pneumococcal Disease (IPD), pneumonia and acute otitis media caused by *S. pneumoniae* in infants, children and adolescents from 6 weeks to 17 years of age, and in the United States in February 2010 for the prevention of IPD and otitis media caused by *S. pneumoniae* in children 6 weeks through 5 years of age.

13vPnC is in use in the national childhood immunization programs in many countries and contains polysaccharides from the 7 serotypes included in the original 7vPnC (4, 6B, 9V, 14, 18C, 19F, and 23F) and an additional 6 serotypes (1, 3, 5, 6A, 7F, and 19A), all conjugated to cross-reactive material 197. It has been shown that the 6 additional serotypes in 13vPnC increase coverage for IPD prevention in children <5 years of age from 74% to 88% globally. Importantly, the additional serotypes in 13vPnC are associated with a high percentage of pneumococcal disease in the developing world. 5,6

In October 2016, 13vPnC was approved in China for the prevention of invasive disease (including bacteremic pneumonia, meningitis, septicemia, and bacteremia) caused by *Streptococcus pneumoniae* for infants and children aged 6 weeks to 15 months. 13vPnC is recommended as a series of four doses, one dose at each of these ages: 2 months; 4 months; 6 months; 12 through 15 months. Vaccines in China are classified into two categories. Type I vaccines are mandatory and provided for citizens by the government free of charge, and infants and children should get immunized according to the government's regulations. These vaccines include tuberculosis (Bacillus Calmette–Guérin), diphtheria/tetanus/ pertussis, oral polio, measles/mumps/rubella, hepatitis B, hepatitis A, meningococcal, and Japanese encephalitis. Type II vaccines are ones available on the private market for use on a voluntary base at the purchaser's expense. They consist of Haemophilus influenzae type b (Hib), pneumococcal conjugate, rotavirus (RV), inactivated polio (IPV), varicella, human papillomavirus, and influenza vaccines. In China, all type I and type II vaccines are

administrated at China Centers for Disease Control and Prevention (CDC) immunization clinics.

13vPnC has a favorable benefit-risk profile. Based on data from clinical trials and the worldwide safety experiences after authorization, convulsions/seizures, fever, apnea, and anaphylaxis/hypersensitivity are identified as known or potential risks associated with 13vPnC among young children.^{7,8}

To monitor these known and potential risks for 13vPnC among Chinese children receiving 13vPnC in China, an observational study using a population-based electronic health record (EHR) database from 1 May 2017 to 31 July 2020 in Yinzhou district of Ningbo city in China is conducted in a real world setting. Yinzhou is one of the largest districts in economically developed Ningbo city. Children exposed to 13vPnC in Yinzhou district are representative of those children likely receiving 13vPnC in China given that only families with sufficient financial resources can afford 13vPnC. In addition, the coverage for 7-valent pneumococcal conjugate vaccine (7vPnC) in Yinzhou district was similar to that in the published literature in China. As a population-based database, Yinzhou EHR database consists of complete immunization records and healthcare data of all children in the district. This allows for the possibility of monitoring the safety of 13vPnC in the context of routine medical care from outpatient visits to inpatient care and provides greater generalizable findings.

This observational safety study is a post authorization commitment (PAC) to fulfill the key monitoring activity requirement of the China National Medical Products Administration (NMPA).

6. RESEARCH QUESTION AND OBJECTIVES

This observational study using a population-based EHR database in Yinzhou district of Ningbo city is to expand the understanding of the safety profile of 13vPnC in Chinese pediatric populations.

Objectives of the study are to:

- Estimate incidence rates (per 1,000 person-days at risk and per 1,000 doses) of safety outcomes of interest (SOIs) including seizures (including febrile seizures), urticaria and angioedema, apnea, and fever for the periods of 0 through 3 days (with 0 indicating the day of vaccination), 4 through 7 days, and 0 through 7 days after the 13vPnC vaccination by all doses and by each dose in the main study based on Yinzhou EHR database between 1 May 2017 and 31 July 2020.
- Estimate the incidence rates (per 1,000 person-days at risk and per 1,000 doses) of SOIs mentioned above for the same periods after the 13vPnC vaccination by all doses and by each dose in a sub-population of the main study through a prospective cohort study between 1 August 2018 and 31 July 2020.

All SOIs are acute events and are likely to occur within 7 days post-vaccination based on the known safety profile of 13vPnC as well as biologic plausibility of these events occurring after vaccination.^{7,8}

7. RESEARCH METHODS

7.1. Study Design

This is an observational study based on a population-based EHR database. In addition, a validation study including validation of International classification of diseases, tenth revision (ICD-10) codes or ICD-10 code based algorithm for identifying all SOIs and a prospective cohort study in a sub-population of the main study will be conducted in order to offset the potential biased results from the main study because of potential misclassification of the SOIs due to miscoding and/or undercoding of ICD-10 codes used to identify the SOIs in the EHR database.

7.2. Study Population

The main study population consists of eligible children aged 1-24 months receiving at least one dose of 13vPnC recorded in Yinzhou EHR database between 1 May 2017 and 24 July 2020 (ie, one week prior to the end of the study) (Figure 1).

[figure not shown]
7.2.1. Inclusion Criteria

To be eligible for the main study, children in Yinzhou population-based EHR database must be aged 1 to 24 months and receive at least one dose of 13vPnC between 1 May 2017 and 24 July 2020 where the first dose is received before or on 24July 2020 since a 7-day post-vaccination follow-up for each dose in each child receiving 13vPnC is needed. For the prospective cohort in a sub-population of the main study, eligible children for the main study must receive the first dose of 13vPnC between 1 August 2018 and 24 July 2020 and an informed consent must be obtained from parents/legal guardians (Figure 1).

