7.5.2. A Prospective Cohort Study in a Sub-Population

A prospective cohort study in a sub-population of the main study was initiated on 1 August 2018 after obtaining the approval of Human Genetic Resources Administration of China (HGRAC) application. The prospective cohort study will end on 31 July 2020. Potential participants are enrolled at the time of a visit to CDC immunization clinics after the informed consent is obtained. An initial questionnaire for the first dose is administered to parents/legal guardians of children in the office by healthcare professionals (HCPs) at the immunization clinics when a child receives the 13vPnC vaccination. A follow-up questionnaire at 7 days post-vaccination is administered by the HCPs either via a telephone or face-to-face interview to parents/legal guardians of the children. The initial questionnaires and follow-up questionnaire are completed for each dose of the 13vPnC vaccination. It should be noted that responsibilities of HCPs at the CDC immunization clinics are to administer vaccines to children and they are not children's treating HCPs.

Both a web-based questionnaire and a paper-based questionnaire are made available to the HCPs for their preference. The HCPs at CDC immunization clinics have access to the web-based questionnaire via their work computers. Based on the feedback from Yinzhou CDC, the HCPs would be likely to use the web-based questionnaire for a face-to-face interview and a paper-based questionnaire for a phone interview. However, if a paper questionnaire is used at an interview, the HCP will be instructed to transfer the data from the completed paper questionnaire by completing a web-based questionnaire. A copy of the completed paper questionnaire will be uploaded to the validation study database. It is expected that completion of the initial questionnaire and the follow-up questionnaire will take approximately 20 minutes and 15 minutes respectively.

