7.7. Data Management

All data for the main study are collected through the routine data collection practices of the Yinzhou EHR database. The data in the Yinzhou EHR database are updated continually. The principal investigator or his delegates at Fudan University will have access to de-identified study specific data generated by the data builder and manager of the Yinzhou EHR database (Wanda Inc) via a secure server. Data for the main study will be stored in the form of SAS® datasets at the secure server.

Data obtained from the validation study will also be housed and managed by Wanda Inc. Fudan University and Pfizer have full access to the de-identified study database. Although identifiable data such as children's NID numbers, their dates of birth, their names, etc. will be collected in one part of the validation study (ie, the prospective cohort study in a sub-population of the main study), these identifiable data will only be used by Wanda Inc to link children who participate in both the main study and the validation study for the purpose of analyses. The identifiable data will not be shared with Fudan University, Pfizer, or other third parties.

The first annual progress report to NMPA presented the study status since the HGRAC application for the study was pending. To prepare the subsequent annual progress reports to NMPA, the main study database is to be queried to identify the number of eligible children who have received a 13vPnC vaccination. For these children, routinely collected data are abstracted for the study variables: demographics; medical history; coadministration of other type I and type II vaccines if any, and the SOIs. Counts of the study variables in the main study will be included in the 2019 progress report and descriptive analyses will be conducted for the 2020 progress report.

Eligible children are followed in the Yinzhou EHR from the date of the first dose of the 13vPnC vaccination until 7 days after the last dose of the 13vPnC vaccination, moving out of the district, death, loss to follow-up, or the end of the study (whichever occurs first) for the occurrence of the SOIs.

All data will be maintained by a trained group of data managers from Wanda Inc ensuring compliance with national regulations in China. SAS® will be used for the statistical analyses.

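### The 24 July 2020 cut-off binds only the first dose, although its stated reason is seven days of follow-up for every dose (minor)

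*Protocol*

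**What the plan says.** Protocol Section 7.2.1 gives the limit and its reason in one clause: "where the first dose is received before or on 24July 2020 since a 7-day post-vaccination follow-up for each dose in each child". Section 7.2 repeats 24 July 2020 as the last date for receiving at least one dose and explains that it lies a week before the study closes. The cohort has the same first-dose limit, with entry from 1 August 2018.

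Four other places bear on later doses:

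- Section 6 asks for rates "by all doses and by each dose in the main study based on Yinzhou EHR database between 1 May 2017 and 31 July 2020", per 1,000 person-days and per 1,000 doses.
- Section 7.2.2 states that there are no exclusion criteria.
- Section 7.7 ends follow-up a week after the final dose or at an earlier stop: "moving out of the district, death, loss to follow-up, or the end of the study (whichever occurs first").
- Section 7.5.2 schedules a follow-up questionnaire at 7 days after each dose and says: "The prospective cohort study will end on 31 July 2020".

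No section gives a last date for doses 2, 3 or 4.

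**The concern.** The rule and its reason refer to different units. A rule that protects the follow-up of each dose should limit each dose, but this one limits entry of the child. Section 5 describes a four-dose series, so a child first vaccinated in, say, March 2020 can receive a later dose in the last week of July 2020 and remain eligible. Follow-up of that dose is cut at 31 July.

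A person-day rate absorbs this, because the unobserved days leave the denominator. A rate per 1,000 doses does not: a dose with one observed day weighs as much as a dose with eight. Any error is downward, affects doses 2 to 4 only, and is largest for days 4-7.

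**Working it through.** **1. The plan's own date.** Day 0 is the day of vaccination, so days 0-7 are 8 calendar days. 24 July + 7 days = 31 July 2020. A dose on 24 July has its whole window inside the study, so the chosen date is correct for any dose to which it is applied.

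**2. Days observed for later dates**, with censoring after 31 July:

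| Dose date (July 2020) | Days 0-7 (of 8) | Days 0-3 (of 4) | Days 4-7 (of 4) |
|---|---|---|---|
| 24 | 8 | 4 | 4 |
| 25 | 7 | 4 | 3 |
| 26 | 6 | 4 | 2 |
| 27 | 5 | 4 | 1 |
| 28 | 4 | 4 | 0 |
| 29 | 3 | 3 | 0 |
| 30 | 2 | 2 | 0 |
| 31 | 1 | 1 | 0 |
| Sum, 25-31 | 28 of 56 | 22 of 28 | 6 of 28 |

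The observed fractions p are 0.50, 0.786 and 0.214.

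**3. Effect on the main-study rates per 1,000 doses, doses 2 to 4.** Let f be the share of these doses given on 25-31 July. With a constant hazard within each window, the expected per-dose rate is multiplied by 1 − f(1 − p), so the relative shortfall is f(1 − p).

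The protocol does not give f. Assume first an even flow over 1 May 2017 to 31 July 2020 (1,188 days): f = 7/1,188 = 0.59%.

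- Days 0-7: 0.59% × 0.50 = 0.29%
- Days 0-3: 0.59% × 0.214 = 0.13%
- Days 4-7: 0.59% × 0.786 = 0.46%

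With twice that flow in the last week (f = 1.18%), the shortfalls are 0.59%, 0.25% and 0.93%.

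**4. Is double flow a reasonable upper case?** Section 7.6 reports about 10,000 children by 30 January 2019 (640 days) and projects about 22,000 in total. That implies 12,000 over the remaining 541 days to 24 July 2020. The later accrual rate is 12,000/541 = 22.2 per day, against an average of 22,000/1,181 = 18.6 per day, a ratio of 1.19. Dose 4 also starts later. If it is given about 11.5 months after dose 1 (an assumption), it accrues over 27.5 of the 39 months, and its share in the last week (0.23 month) is 0.23/27.5 = 0.84%. Double flow (1.18%) lies above 0.84%, and also above 0.84% × 1.19 = 1.00%.

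**5. Number of doses.** With 22,000 children and an assumed 1 to 3 later doses each, even flow puts about 130 to 390 doses in that week, or 0.29% to 0.44% of all doses. At double flow it is about 260 to 780 doses, or 0.59% to 0.88%.

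**6. Cohort.** The day-7 questionnaire for doses given on 25-31 July falls on 1-7 August 2020, after the stated cohort end. Assuming even accrual and doses at 0, 2, 4 and 11.5 months after dose 1, accrual time over 24 months is 24 + 22 + 20 + 12.5 = 78.5 months. The affected share is 3 × 0.23/78.5 = 0.9% of cohort doses, and 0.23/12.5 = 1.8% of cohort dose 4. These are shares of doses without a questionnaire, not biases.

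**The case against.** The strongest objection is that nothing in the protocol says late doses are counted. Section 7.2.1 governs which children enter, and Section 7.8 names the per-dose rate without a counting rule. The stated need for follow-up of each dose could lead an analyst to drop doses that lack it. Section 7.8 also leaves detailed methods to the SAP, which is not at hand. This stands to the extent that counting late doses is the default reading, not an explicit instruction. It does not remove the point. The protocol itself fixes the cut-off and its reason, and attaches the date to the wrong unit. An SAP that follows the text would keep these doses, and one that drops them would depart from it.

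A reader might infer that these doses have no outcome follow-up at all. The documents do not support that. In the EHR every such dose has at least day 0 observed, and only the days 4-7 window for doses on 28-31 July has no observed day. Cohort children also belong to the main study and can be linked to it (Section 7.7), so they have EHR data as well.

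A reader might also infer that the cohort rates are biased. That would follow only if a dose without a follow-up questionnaire were counted as event-free, and no section says so. As written, such doses are missing questionnaire data.

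Finally, the effect is far below sampling error. With an assumed 1 to 10 events per 1,000 doses and 22,000 to 88,000 doses, the event counts are 22 to 880. The approximate 95% half-widths, 1.96/√events, run from 42% down to 7%. That objection stands, and it is why the point is minor.

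**Conclusion.** The cut-off is inconsistent with its own reason: it should bind each dose and binds only the first. On the default reading, the main-study rates per 1,000 doses for doses 2 to 4 are too low by about 0.3% (days 0-7), 0.1% (days 0-3) and 0.5% (days 4-7) in relative terms, and by about 1% or less at double flow. This rests on an assumed dose flow, a constant hazard within each window, and late doses being counted. Person-day rates are not affected. In the cohort the consequence is missing questionnaires for a small share of later doses.

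It would go too far to say that this distorts a planned comparison between doses or damages a leading endpoint. Section 7.8 makes all analyses descriptive, no test between doses is planned, and Section 6 ranks neither rate scale above the other. This is a minor consistency defect that does not threaten the conclusions, and it is worth correcting because it is easily avoided.

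**What to change.** In Sections 7.2.1 and 7.7, state that a 13vPnC dose of any number enters the rates only if it was given on or before 24 July 2020, in both the main study and the cohort. Every counted dose then has its full 8, 4 and 4 window-days inside the study. The cost is one sentence and, under even accrual, fewer than about 1% of doses overall.

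Alternatively, keep doses through 31 July and follow outcomes to 7 August 2020. The last main-study data cut is 30 September 2020 (Section 4), so the EHR data would be available and no dose would be lost. The cohort end date in Section 7.5.2 would need the same extension, so that the day-7 questionnaires for those doses fall within the study.

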7.2.2. Exclusion Criteria

There are no exclusion criteria for this study.

Figure 1. Flow Chart for Study Populations

7.3. Variables

The exposure of interest is 13vPnC vaccine administered in CDC immunization clinics in Yinzhou district. SOIs are seizures, urticaria and angioedema, apnea and fever. Dates and doses of 13vPnC vaccination are recorded in Yinzhou CDC Immunization Administration Registry which is integrated into Yinzhou EHR database at an individual level. SOIs are documented in Yinzhou EHR database according to ICD coding in the database except ones in the CDC Adverse Event Following Immunization Information System (AEFIS). The events in AEFIS are recorded in text format based on a diagnosis. Variables and their descriptions are shown on Table 1. ICD codes or algorithm of ICD codes and diagnoses used to identify the SOIs in the study will be developed and documented in the statistical analysis plan (SAP).

Table 1. Variables and Roles

Variable	Role
Age at each dose of 13vPnC vaccination	Demographic
Gender	Demographic
Residency Status	Demographic
Smoking in the family (only the prospective cohort in a sub-population)	Covariate
Known allergies (only the prospective cohort in a sub-population)	Medical history
Preterm	Medical history
Low birth weight	Medical history
Sickle cell disease	Medical history
History of febrile seizure	Medical history
History of other seizures	Medical history
History of urticaria	Medical history
History of angioedema	Medical history
History of apnea	Medical history
Fever at the date prior to 13vPnC vaccination	Medical history
Other vaccines administrated the same date with 13vPnC	Co-administration
Season of diagnosis for each safety outcome of interest	Covariate
Hospitalization for each safety outcome of interest	Covariate
Date of each dose of 13vPnC vaccination (based on barcode scanning)	Exposure
Seizures (including febrile seizures)	Outcome
Urticaria and angioedema	Outcome
Apnea	Outcome
Fever	Outcome
Highest temperature for each day fever is reported (only the prospective cohort in a sub-population)	Outcome
Use of antipyretics post-vaccination (only the prospective cohort in a sub-population)	Covariate

